4.1 General Principles

The statistical evaluation will be performed by using the software package SAS release 9.4 (SAS Institute Inc., Cary, NC, USA).

The analysis will be based on the Global Standard Tables (Version 3.0 or higher) and the Clinical Pharmacology Standards (CLIPS) (Version 1.2 or higher) where appropriate.

The validity of subjects for allocation to various analysis sets will be assessed in an ongoing manner in several validity review meetings and decisions will be documented in the validity review reports prior to unblinding (potential conditional validity for per-protocol set [PPS] and pharmacokinetic analysis set [PKS]). This SAP may be updated based on the results of the validity review meetings.

Only adjudicated outcome events will be used for all efficacy analyses except for that specified in section [6.2.3.6](#).

A log-normal distribution is assumed for serum creatinine and UACR. For all other metric variables, a normal distribution is assumed. The distributional assumptions will be investigated and if necessary, nonparametric methods or transformation of the data will be considered.

All variables will be analyzed by descriptive statistical methods. The number of data available, mean, standard deviation (SD), minimum, lower quartile, median, upper quartile, and maximum will be calculated for metric data. The geometric mean and SD will be provided instead of the arithmetic mean and SD for the variables where log-normal distributions are assumed. Frequency tables will be generated for categorical data.

The laboratory parameter eGFR will be calculated based on the CKD-EPI formula for all analyses specified in this SAP.

All subjects will be analyzed according to the planned treatment group in the FAS (the intent-to-treat or ITT principle). All subjects will be analyzed according to the actual treatment in the

safety analysis set (SAF). If a subject receives both treatments due to a bottle error, the treatment actually received for the majority of the time in the study will be used in SAF.

The stratified analyses mentioned in this SAP will be conducted in consideration of the randomization stratification factors region, eGFR category, type of albuminuria and history of cardiovascular disease (CVD) unless specified otherwise, see also section 4.5.4. The strata variables type of albuminuria, eGFR category and history of cardiovascular disease used in the statistical analysis will be based on the screening UACR and eGFR assessments and medical history and corrected via the interactive voice/web response system (IxRS) if necessary. All subjects will be analyzed according to their correct stratification category. If screening values are not available, the run-in values will be used. If a subject's actual UACR / eGFR combination results in a stratification group that does not exist in the study (e.g. in 17530, very high albuminuria and eGFR ≥ 45 to < 60 mL/min/1.73m²) then the stratification group the investigator originally specified in IxRS will be kept.

In case of stratification errors, the primary analysis will also be repeated based on the stratification category used in the randomization as a sensitivity analysis.

4.2 Handling of Dropouts

A subject who has been randomized and discontinues study participation prematurely for any reason is defined as a "dropout", even if no study drug has been taken. Dropouts will not be replaced.

Data from subjects who prematurely terminated the study will be used to the maximum extent possible.

The number of subjects discontinuing the epochs, together with the primary reason for discontinuation, will be summarized as described in section 6.1.1.

The number of subjects who prematurely discontinue the study and/or study treatment for any reason, as well as the reasons for premature discontinuation of study and/or study treatment, will be reported. Kaplan-Meier plots for "Time to end of study" and "Time to end of study treatment" will be provided.

All dropouts and subjects prematurely discontinuing study treatment will be evaluated with respect to

- baseline characteristics
- potential differences between the treatment groups in the proportion of patient withdrawals or in the timing of withdrawals
- the reasons for premature discontinuation of study and/or study treatment.

4.3 Handling of Missing Data

All missing or partial data will be presented in the subject data listing as they are recorded on the Case Report Form (CRF).

General rules

When appropriate, the following rules will be implemented so as not to exclude subjects or observations from statistical analyses due to missing or incomplete data.

Concomitant medications with missing start and stop date but flagged as being ongoing at end of study will be considered to have started prior to study medication start and end after stop of study medication. The start and end reference period will be imputed as “before” for the medication start and as “during/after” for the medication end.

In case of (partially) missing dates for interruptions or permanent stop of study medication intake, a ‘worst-case’ approach will be applied to impute the start and end dates of study medication intake as the minimum and maximal possible dates, i.e.:

- first month of the year, or first day of the month for a partially missing start date, and
- last month of the year, or last day of the month for a partially missing end date.

If a subject died earlier than the imputed worst study medication end date, the death date will be taken as the study medication end date. However, if these imputations lead to a temporal overlap between different exposure date records, the imputed dates will be adjusted so that no overlap exists and the time on the higher dose is maximized. The date of first exposure to treatment is not expected to be missing as the patients are instructed by the investigator to take their first dose of study drug directly at Visit 1, but in the very rare case that this date is not recorded, it will be imputed according to the rules outlined above for missing start dates, but not earlier than the randomization date.

When only partial dates are available for clinical events in the efficacy analysis, a median imputation rule will be used:

- For example if the day is missing and the month is July, then day 16 is chosen.
- If the number of potential values is even, the lower of the 2 middle numbers is taken. For example, if the day is missing and the month is June, then day 15 is imputed. The same rule applies if the day and month are missing, e.g. if the year is 2017 and the day and month are missing, 2nd July is taken.
- In case the range of possible values is further restricted, e.g. because a patient died in the month in which the day is missing, the median in the restricted set of possible values is calculated. For example, if the clinical event occurred in June 2017 and the respective patient died on 11th June 2017, 6th June 2017 is imputed as the date of the clinical event.

The same principle also applies to partially missing death dates, e.g. if only the year of death is available, but there is a last contact in the given year, then the date of death is imputed as the median of this date and the end of the given year.

In case a death date is completely missing, it will be imputed on the basis of the last known contact when the subject was still alive and the first known contact when the subject was dead (e.g. from the subject health status follow-up page) as the median of these two dates. As above, if the number of potential values is even, the lower of the two middle numbers is taken.

In case both a non-fatal clinical event and death have partially missing dates, then death takes precedence and will be imputed first according to the rules outlined above. This also applies for non-renal and non-CV death.

However, given the importance of an accurate determination of the adjudicated event date in relation to randomization date for the time to event analysis, we would expect a minimal number of such missing dates.

For the analyses of the secondary endpoint UACR at Month 4, the closest post-baseline set of measurements to day 120 (+/-30days) will be taken as Month 4. If there is no set of measurements within this time frame, the subject will be excluded from the primary analysis of UACR at Month 4.

A worst case approach will be applied for determining whether an AE with partially missing dates is treatment-emergent or not, i.e. if it is possible that the adverse event start date is within a period of study drug intake +3 days, then the adverse event is considered treatment-emergent.

If intensity of the AE is missing, the event will be considered as severe. If the same event is reported as both unrelated and related to the study drug within a subject, the event will be reported as related to study drug. If the drug relationship is missing, the event will be considered as being related to the study drug.

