Furthermore, the dose status will be summarized with absolute and relative frequencies per treatment group for each visit with regard to the question “Was 20 mg study drug dispensed at visit?” and the reason why 20 mg was not dispensed. The number of subjects not dispensed with 20 mg as well as associated reason will also be presented overall, i.e. on the patient level. Number of subjects on 10 mg, 20 mg or on an interruption at Day 1, Month 1, Month 4 and in 4-monthly intervals from then onwards will also be derived based on exposure information and presented by treatment group.

In addition, the number of patients with study drug down-titrated to 10 mg or temporarily interrupted (dose recorded as 0 mg) as well as associated reason will be summarized with absolute and relative frequencies per treatment group.

The compliance (as percentage) will be calculated as follows:

$$100 * \text{Number of taken tablets} / \text{Number of planned tablets}$$

The number of planned tablets is calculated as follows:

(Days from randomization to last intake of study drug + 1) * Number of planned tablets per day.

All tablets, including the dummy placebo tablets, will be counted. For subjects who withdraw prematurely from the study drug, compliance will be calculated up to the time of last dose.

The compliance will be summarized descriptively by treatment group and overall. In addition, percent of compliance will be categorized into 3 groups, less than 80%, 80 to 120% and greater than 120%, and the categories will be summarized by treatment group and overall.

Further analyses will be performed to evaluate the impact of the COVID-19 pandemic on the intake of study drug and on visits that were not performed as per protocol:

- The number of subjects with missing visits or visits not performed as per the study protocol will be summarized by treatment group and differentiated by COVID-19 pandemic-related reason (FAS).
- The duration and frequency of interruptions related to the COVID-19 pandemic will be shown by treatment group for any COVID-19 pandemic-related reason and for each more specific reason (SAF).
- Number of subjects not dispensed with 20 mg for any reason including COVID-19 pandemic-related reason will be summarized in relation to the number of subjects attending the respective visits (SAF).
- A listing of all treatment interruptions associated with COVID-19 will be provided along with the reason for dose adjustment.

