An ‘on-treatment’ analysis will also be performed, repeating the Kaplan Meier estimates and curves as well as the inferential statistics (stratified logrank test and stratified Cox regression model) on the FAS. For the on-treatment analysis, as described for the PPS analysis above, the censoring rules for the primary analysis will be adapted by further restricting to events occurring up to 30 days after last study drug intake.

The logrank test as well as the Cox regression model will also be performed without including stratification factors. The plausibility of the proportional hazards assumption will be assessed by visually examining the plot of the log of the negative log of Kaplan-Meier estimates of the survival function versus log time for evidence of non-parallelism, and by including a treatment by log-transformed time interaction into the Cox model. For the latter, the SAS code is adapted as follows:

```
PROC PHREG DATA = <dataset>;
  MODEL ttevalue * ttecnsr(1) = trtgrpnr trtltime / RL
  TIES=EFRON ALPHA=0.05;
  STRATA {stratum};
  trtltime = trtgrpnr*log(ttevalue);
RUN;
```

The significance of the interaction will be tested at the 5% type I error level. If the interaction is significant and there is strong evidence of non-proportionality from the plots, time-dependent hazard ratios will be estimated with the model that includes the interaction term.

The censoring mechanism of subjects without an event of the primary composite endpoint at the time of analysis is assumed to be non-informative for the primary efficacy analysis. This also implies that the primary analysis is valid under a missing at random (MAR) assumption. Sensitivity analyses will be performed, assessing the impact of a potential informative censoring of subjects lost to follow-up or with withdrawn consent. Non-CV deaths will be treated as censored observations as in the primary analysis.

A summary of the amount of missing data by treatment arm will be given, including number of subjects who have incomplete follow-up on the respective endpoint as well as the ratio of the observed follow-up time to the expected follow-up time for the respective endpoint.

Robustness with respect to missing data will be investigated with a tipping point analysis on the FAS (based on the ITT approach). The analysis will:

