- Number of subjects discontinuing study drug permanently due to worsening of renal function

These will be summarized by treatment group using frequency counts. For the number of subjects with these events, the summary will be provided once for all events and once for all treatment-emergent events.

Cumulative incidences based on Aalen-Johansen estimates (including 95% confidence intervals) [14] and accounting for mortality as competing risk will be provided for the time to first treatment-emergent hyperkalemia event (any, leading to hospitalization and leading to permanent discontinuation of study drug). For this analysis, the person-time at risk for a single subject is the number of days from first intake of study drug until the event of interest or until the minimum of (date of death, last exposure to treatment +3 days) excluding temporary study drug interruptions (i.e. the time between start of a temporary study drug interruption + 3 days until the end of the interruption).

Furthermore, concomitant medications taken as treatment for treatment-emergent hyperkalemia will be shown by treatment group and overall.

Separate tables summarizing TEAEs, study drug-related TEAEs, and SAEs that occurred in more than 5% of the subjects will be provided.

Deaths, SAEs and AEs leading to permanent study drug discontinuation will be listed separately.

In addition, subjects with a COVID-19 adverse event will be summarized and listed. The number of subjects affected by the COVID-19 pandemic and experiencing treatment-emergent adverse events since the country-specific COVID-19 onset date will also be summarized, along with a listing of all adverse events since the country-specific COVID-19 onset date of subjects with a COVID-19 infection.

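### A partly missing study-drug stop date is imputed to month or year end and capped only at death, so drug intake and safety time at risk can run past the EOS visit or last contact

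*SAP*

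**What the plan says.** SAP 4.3 states the rule: "In case of (partially) missing dates for interruptions or permanent stop of study medication intake, a ‘worst-case’ approach will be applied". Imputed start dates go to the earliest possible date and end dates to the latest. For an end date the latest date is spelled out as the "last month of the year, or last day of the month for a partially missing end date".

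Two limits follow. The first is death: "If a subject died earlier than the imputed worst study medication end date, the death date will be taken" as the stop date. The second concerns multiple records: "if these imputations lead to a temporal overlap between different exposure date records, the imputed dates will be adjusted so that no overlap exists", with time on the higher dose maximised. Neither the EOS visit nor last contact is named.

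The resulting date is used in several places:

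- **SAP 6.1.5, treatment duration:** runs from start to permanent stop of study drug.
- **SAP 6.1.5, compliance:** planned tablets are ("Days from randomization to last intake of study drug + 1) * Number of planned tablets per day". SAP 5.3 excludes a subject from the PPS when compliance is below 80%.
- **SAP 6.4.1 and 6.4.2, Aalen-Johansen curves for hyperkalaemia and potassium:** time at risk runs to the event or "until the minimum of (date of death, last exposure to treatment +3 days"), less temporary interruptions.
- **SAP 6.2.1.2, on-treatment and PPS efficacy:** the primary censoring rules are kept and narrowed by "further restricting to events occurring up to 30 days after last study drug intake".

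**The concern.** Subjects still on treatment stop drug at the EOS visit (SAP 3), and nothing can be recorded after last contact. A stop date later than either is therefore impossible or unobservable, yet the rule can produce one. The overlap adjustment does not help with a permanent stop, because no later exposure record follows it.

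The rule errs on the side of caution when deciding whether an adverse event or laboratory value is treatment-emergent. The same date has the opposite effect in a denominator. In the Aalen-Johansen analyses, a subject kept in the risk set after last contact cannot contribute an event, so the estimated incidence falls. Protocol 9.7.1 names hyperkalaemia as one of the main risks seen with this drug class, so this is the safety result where a downward bias is least welcome.

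The SAP uses last contact as a bound elsewhere: for partly missing death dates (4.3), for primary censoring (6.2.1.1), and for time at risk for investigator-reported outcome events (6.2.3.6). Drug stop dates, and the safety time at risk built on them, are the exception.

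**Working it through.** The plan states no figure for this excess, so there is none to reproduce. The check is calendar arithmetic on the SAP 4.3 rule.

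**1. Excess intake after last contact.** Excess E = imputed stop date − last contact, with last contact inside the recorded stop year or month.

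| What is recorded | Imputed stop | Maximum E | Mean E if last contact is uniform over the period |
|---|---|---|---|
| Year only | 31 December | 364 days (365 in a leap year) | 182 days (182.5) |
| Month and year (31-day month) | Last day of month | 30 days | 15 days |

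Safety time at risk adds 3 days, so with a year-only date it can run 367 days (368 in a leap year) past last contact.

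**2. One illustrative subject** (dates assumed): randomised and started 1 July 2017, last contact 10 January 2018, one tablet a day to last contact.

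- Observed duration: 193 + 1 = 194 days.
- Stop recorded as 2018: imputed 31 December 2018, E = 355 days, duration 194 + 355 = 549 days. Time at risk ends 3 January 2019, 358 days after last contact.
- Compliance = 100 × 194 / 549 = 35.3%, below the 80% limit.
- Stop recorded as January 2018: imputed 31 January 2018, E = 21 days, compliance = 100 × 194 / 215 = 90.2%, above the limit.

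**3. When compliance crosses 80%.** For a fully adherent subject with D observed days, D / (D + E) ≥ 0.80 requires D ≥ 4E. With E = 364, D must be at least 1456 days; with E = 30, at least 120 days. A late year-only error therefore excludes nearly any subject, while a day-only error matters only early in treatment.

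**4. Overall size.** Assumptions not in the documents: a fraction f of subjects has a year-only stop date, f from 0.1% to 2%, and mean treatment time T is 2 to 3 years. N = 7400 is the approximate enlarged sample size in SAP 3.

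- Excess person-years = N × f × E / 365.25.
- At the mean E of 182 days: 7400 × 0.001 × 182 / 365.25 = 3.7, rising to 73.7 at f = 2%.
- At the maximum E of 364 days: 7.4 to 147.5.
- Share of exposure = f × (E / 365.25) / T: from 0.001 × 0.498 / 3 = 0.017% to 0.02 × 0.997 / 2 = 1.0%.

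**5. Efficacy.** SAP 6.2.1.1 censors at last contact up to and including the EOS visit. SAP 6.2.1.2 only narrows this for the on-treatment and PPS analyses, so a late stop date cannot move censoring beyond last contact. It can widen the 30-day window in a subject who stopped drug but is still followed, so that an event more than 30 days after the true stop counts as on-treatment.

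**The case against.** **The rule is already bounded.** SAP 4.3 speaks of the latest possible date and applies its rules where appropriate; a date after the EOS visit is not possible. This does not stand, because the text goes on to define the latest date as month or year end and then writes out the limits it wants.

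**The mechanism is guessed.** A reader might infer that incomplete stop dates cluster in subjects lost to follow-up. Neither document says so. Dose changes and stops must be recorded in the eCRF, and accountability is checked at visits. A partial date must have been reported by someone, perhaps at a contact in a later year, in which case year end is not after last contact. A subject who vanished may have no stop date at all. This objection stands.

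**The PPS effect is uncertain.** The 35.3% assumes tablets taken are known and counted only to last contact. If bottles were not returned, the numerator is unknown too. PPS assignment also passes through validity review meetings. This stands: PPS exclusion is possible, not established, and the PPS is supportive.

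**The rule is cautious in other uses.** It widens capture of treatment-emergent events and laboratory values, and counting off-drug time as on-treatment would usually dilute a benefit. This stands, and the SAP history records the choice as conservative. It does not cover the denominators.

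**The effect is small and the rule is the same in both arms.** This stands as to size, and the affected curves are descriptive. It is no reason to leave impossible dates in the derivation.

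**Conclusion.** The point holds in a limited form. As written, SAP 4.3 can place study-drug intake after the EOS visit or last contact: by up to 364 days (365 in a leap year) with a year-only date, and by up to 30 days when only the day is missing. Treatment duration is then overstated, the compliance denominator can be inflated, and the hyperkalaemia and potassium cumulative incidences are biased slightly down.

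A reader might infer that the efficacy results are affected in the same way. The documents do not support that. The primary analysis does not use the stop date, and on-treatment and PPS efficacy time remains bounded by last contact. The remaining efficacy effect is that some off-drug events may be counted as on-treatment in subjects still followed.

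The number of incomplete dates is not stated. Under the assumed 0.1% to 2% with year-only dates, the excess is about 0.02% to 1.0% of exposure, so the overall effect is probably small. This is a low-priority correction, worth making because it is cheap and the bias runs the wrong way for a key safety outcome.

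**What to change.** In SAP 4.3, add that an imputed study-drug stop date is no later than the earliest of death, EOS visit and last contact. Both of the last two are needed, because a post-treatment contact can follow the EOS visit. In SAP 6.4.1 and 6.4.2, end time at risk at the minimum of death, last exposure + 3 days, and last contact.

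In the illustrative subject this returns duration from 549 to 194 days and compliance from 35.3% to 100%, and leaves no time at risk after last contact.

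The cost is two sentences and one programming cap, with no new data. The downside is that any tablets taken after last contact are not counted, although subjects do leave visits with dispensed drug. A separate midpoint date for the efficacy windows or compliance is not needed; it would give one subject two different stop dates.
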